9. Willing to cooperate with all study procedures during the research period.

Participants will be **excluded** from the study if they meet the following criteria:

1. Severe hearing impairment.

2. Unstable vital signs or unclear consciousness.

III: Sample Size Calculation

The sample size was estimated based on the **Generalized Estimating Equations (GEE)** approach for repeated measures. The analysis will control for baseline demographic and disease characteristics as covariates (e.g., age, sex, education level, occupation, perceived economic status, marital status, religious beliefs, and metastasis). The dependent variables are fatigue, White Blood Cell (WBC) count, hemoglobin, and albumin.

The calculation was performed using G*Power software (version 3.1.9.7). Parameters were set as follows: a significance level (α) of 0.05, statistical power ($1-\beta$) of 0.80, a 95% confidence interval, and an anticipated **effect size of 0.21**. This calculation yielded a required sample size of 34 participants (as shown in Figure 3-2). To account for a potential attrition rate of 30%, the study aims to recruit a total of **44 participants** ($n=22$ for Group A, $n=22$ for Group B).

Music Therapy Protocol

1. Music Selection, Dosage, and Headphone Use

According to the literature, a music therapy duration of 15–30 minutes is effective for fatigue alleviation (Burns et al., 2008; Cassileth et al., 2003; Miladinia et al., 2021; Reimnitz et al., 2020; Sezgin & Bektas, 2022). Music selection will be based on individual preferences and cultural background (Tsai & Chou, 2015; Browning, 2000; Gerdner, 2000).

To ensure data integrity while considering the patient's length of stay, physical burden during chemotherapy, and protocol adherence, the music therapy intervention in this study will be administered **once daily for 21 consecutive days**. The **30-minute intervention** will commence at the start of the chemotherapy infusion. During the study, participants will be provided with a chemotherapy symptom tracking diary to confirm adherence to the music therapy protocol in the experimental group.

For reasons of personal hygiene, preference, and potential patient discharge, participants will be asked to use their own headphones. If a participant does not have headphones, a set will be provided by the researcher.

Research Instruments and Psychometric Properties

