1. Participant Demographic Data Sheet Data will be collected using Google Forms or paper questionnaires, as appropriate. This sheet includes demographic information such as age, sex, education level, occupation, perceived economic status, marital status, and religious beliefs, to be completed by the participant. The questionnaire also

includes items regarding the participant's prior musical training, frequency of daily music listening, motivations for listening, typical timing and methods of listening, and preferred activities during rest.

2. Leukemia-Related Treatment Data Sheet This data will be extracted from the patient's medical records by the researcher. It includes information on chemotherapy drugs and dosages, as well as laboratory values—specifically Absolute Neutrophil Count (ANC), Hemoglobin (Hb), and Albumin—from before chemotherapy (T0) and on Day 21 (T1).

3. Tang Fatigue Rating Scale (TFRS) While many reliable and valid fatigue scales exist globally, many have limitations. Considering that fatigue assessment should encompass physical, psychological, and activity dimensions, the TFRS was selected as the primary outcome measure for this study.

The TFRS contains 37 items across three subscales: Physical (15 items), Psychosocial (12 items), and Daily-Living (10 items). It uses a 10-point rating scale, where higher scores indicate greater fatigue severity. The TFRS underwent content validity testing by three PhD-level experts in fatigue theory and psychometrics. It was validated in a sample of 107 patients with chronic heart failure. The internal consistency (Cronbach's α) was 0.96 for the total scale, and 0.83 (Physical), 0.92 (Psychosocial), and 0.97 (Daily-Living) for the subscales. The TFRS demonstrated excellent validity: **convergent validity** with the Visual Analogue Scale for Fatigue (VAS-F) was 0.87, and **construct validity** with The Beck Depression Inventory-Second Edition (BDI-II) was 0.77 (Tang et al., 2010).

In the study by Tang et al. (2010), the TFRS also showed a significant positive correlation with the New York Heart Association (NYHA) functional class ($r = 0.75, p < 0.01$) and significant negative correlations with Ejection Fraction (EF) ($r = -0.46, p < 0.01$) and Hemoglobin (Hb) ($r = -0.27, p < 0.01$) (Tang et al., 2010).

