Prior to study commencement, approval will be obtained from the Institutional Review Board (IRB). Following IRB approval, and after explaining the study to and receiving consent from the attending physicians and ward nursing staff, the researcher will conduct participant recruitment in the inpatient wards and outpatient clinics. Individuals who meet the inclusion criteria will be identified as potential participants. The researcher will explain the study's purpose and methodology to these individuals. After obtaining informed consent and a signed consent form, the researcher will administer the pre-test (T0) questionnaires. This packet includes the Demographic Data Sheet, the Tang Fatigue Rating Scale (TFRS), the G-8 screening tool, and the symptom diary. This self-administration process is expected to take approximately 10 minutes. If a participant is unable or unwilling to self-report (e.g., due to advanced age or fatigue), the researcher will conduct a structured interview to complete the questionnaires, which is estimated to take 30–40 minutes. Concurrently, all participants will be invited to join the study's official LINE group for communication. Following the collection of baseline questionnaires, a computer-generated randomization sequence will be implemented by personnel not directly involved in the study (i.e., someone other than the principal investigator) to allocate participants to either the experimental group (Group A) or the control group (Group B). Participants in Group A, after confirming their chemotherapy infusion line is properly connected, will begin listening to 30 minutes of self-selected music while concurrently receiving standard care. Participants in Group B will receive standard care only. A total of **60 participants** with Acute Myeloid Leukemia (AML) undergoing chemotherapy are expected to be recruited (n=30 per group). Both groups will be required to complete the symptom diary throughout the 21-day

study period (est. 1 minute per entry). Group A will complete the Fatigue Numerical Rating Scale (NRS) immediately following each music therapy session. Group B will complete the Fatigue NRS 30 minutes after the commencement of their chemotherapy infusion.

On Day 21 (T1), the researcher will collect the post-test data (TFRS, NRS, and G-8) in the ward. If a participant has been discharged, data will be collected via telephone interview or an online questionnaire.

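### The covariate list is open-ended, long for about 31 evaluable patients, and names metastasis, which no described form records; fix a short set built on the baseline outcome and name the tested term

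*Combined protocol and SAP*

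**What the plan says.** Under III: Sample Size Calculation, the plan states: "The analysis will control for baseline demographic and disease characteristics as covariates (e.g., age, sex, education level, occupation", and the list continues to "occupation, perceived economic status, marital status, religious beliefs, and metastasis". That makes eight examples, seven demographic and one disease-related. They are introduced by e.g., so the set is open. The T0 value of the outcome is not among them.

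Under Research Instruments, the demographic sheet carries the seven demographic items: "age, sex, education level, occupation, perceived economic status, marital status, and religious beliefs, to be completed by the participant". Of the treatment data sheet the plan says "It includes information on chemotherapy drugs and dosages, as well as laboratory values", and the values specified are ANC, Hb and albumin. Neither sheet names metastasis, and neither does Table 1. Eligibility is restricted to AML.

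Baseline G-8 is collected (the T0 packet holds "the Tang Fatigue Rating Scale (TFRS), the G-8 screening tool, and the symptom diary") and is repeated at Day 21. It is not named as a covariate.

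The Inferential Statistics paragraph says that GEE will compare pre- and post-test values between the groups. It does not mention covariates, their coding, the model term to be tested, the variance estimator or any small-sample correction.

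**The concern.** Seven or eight covariates, several of them multi-category, are a heavy load for a trial of this size. Covariates unrelated to the outcome use up residual degrees of freedom and widen the true uncertainty of an adjusted group effect. An uncorrected sandwich standard error does not register that widening, so the test rejects too often. The covariate most likely to help, the patient's own T0 value, is not listed. One listed item has no described source. Because the list is open and the tested term is unstated, both could be settled after the data are seen.

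**Working it through.** **1. The plan's own figure.** N = 34 reproduces as a repeated-measures within-between interaction with f = 0.21, k = 2 groups, m = 4 measurements and ρ = 0.5 (m and ρ are assumed, being unstated). λ = f²·N·m/(1−ρ) = 0.0441 × 34 × 4 / 0.5 = 12.0 on (3, 96) df, power 0.823. No covariates enter this calculation.

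**2. Patients available.** 34 × 1.3 = 44.2, the stated 44. After 30% loss, 44 × 0.7 = 30.8, about 31. Research Procedures gives a target of 60 instead, and 60 × 0.7 = 42. So 34 is the required number, not what attrition leaves.

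**3. Covariate degrees of freedom.** The seven demographic items entered as one term each take 7, and metastasis makes 8. If education, occupation, economic status, marital status and religion have 3 to 4 levels each (assumed), they take 10 to 15, so with age and sex the total is 12 to 17. The runs used 7, 8 and 14.

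**4. Expected loss of precision, Day 21 adjusted for T0.** With p noise covariates, the variance is multiplied by (n−4)/(n−4−p).
- n = 34: p = 7 gives 30/23 = 1.304; p = 8 gives 30/22 = 1.364; p = 14 gives 30/16 = 1.875. Square roots: 1.14, 1.17, 1.37.
- n = 31: 27/20 = 1.350; 27/19 = 1.421; 27/13 = 2.077. Square roots: 1.16, 1.19, 1.44.
- n = 42: p = 8 gives 38/30 = 1.267; p = 14 gives 38/24 = 1.583. Square roots: 1.13, 1.26.

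**5. Null simulation.** 3,000 runs per cell, Gaussian GEE, exchangeable working correlation, uncorrected sandwich standard error, cut-off 1.96, correlation 0.5, covariates unrelated to the outcome, dropout completely at random. Each cell shows the empirical SE in outcome SD units, then the rejection rate.

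| Tested quantity | Sample | No covariates | 7 df | 8 df | 14 df |
|---|---|---|---|---|---|
| Day 21, adjusted for T0 | 34 | 0.299; 6.5% | 0.343; 12.4% | 0.353; 13.4% | 0.413; 20.2% |
| Day 21, adjusted for T0 | 31 of 44 | 0.316; 7.8% | 0.380; 14.8% | 0.385; 15.2% | 0.458; 23.9% |
| Days 7/14/21, adjusted for T0 | 34 | 0.228; 7.5% | 0.260; 12.6% | 0.263; 13.8% | 0.310; 20.2% |
| Days 7/14/21, adjusted for T0 | 44, 30% missing Day 21 | 0.203; 7.1% | 0.222; 10.2% | 0.228; 11.5% | 0.256; 15.8% |
| Group-by-time, T0/T1 | 34 | 0.349; 7.0% | 0.348; 7.5% | 0.343; 6.8% | 0.351; 6.9% |
| Group-by-time, T0/T1 | 44, 30% loss | 0.349; 6.5% | 0.355; 6.9% | 0.361; 7.5% | 0.359; 7.8% |

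The smallest SE increase for an adjusted group effect is 0.222/0.203 = 1.09 and the largest is 0.458/0.316 = 1.45. For group-by-time the largest is 0.361/0.349 = 1.03. Monte Carlo error in the rejection rates is about 0.4 to 0.8 points.

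**6. Source of the inflation.** The same Day 21 regressions with a model-based t test reject 4.3% to 5.4% of the time, at every covariate count. The excess therefore comes from combining many covariates with an uncorrected sandwich variance. Dropping the covariates alone still leaves 6.5% to 7.8%.

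**7. Short set against the alternatives.** A separate check at N = 34 under the same assumptions gives an SE of about 0.31 for Day 21 adjusted for T0 and one further covariate. The pre/post contrast gives about 0.34, and the model with 14 extra df about 0.41. By hand, without covariate noise, the T0-adjusted SE is √(0.75 × 4/34) = 0.297 and the pre/post SE is √(1 × 4/34) = 0.343, which agrees.

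**8. G-8.** With an assumed correlation of 0.5 with the person effect, adding G-8 to a model that already holds T0 moves the SE from 0.299 to 0.298 (Day 21) or from 0.228 to 0.221 (three visits).

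**The case against.** The strongest reply is that comparing pre- and post-test values between groups most naturally means a group-by-time term, and the reproduction of N = 34 as an interaction fits that reading. On that contrast time-constant covariates do almost nothing, as the last two rows of the table show. This stands, and it limits the concern. It does not settle the matter, because the plan never names the term. The first hypothesis, lower fatigue during chemotherapy, and the NRS at Days 7, 14 and 21 also permit an adjusted or averaged group effect.

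Three stronger readings are tempting and are not supported:

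- *The planned test has a false-positive rate near 20%.* That needs an adjusted group effect and an uncorrected sandwich variance, and the plan states neither. The covariates in the simulation were also non-prognostic; prognostic ones would recover some precision.
- *G-8 has been excluded, at a cost in precision.* The list is open, so G-8 is unnamed rather than ruled out. The plan describes it only as a vulnerability screen, and its gain beyond T0 was negligible in simulation.
- *Adjustment for metastasis is impossible.* The data sheets are described with inclusive wording, and disease data come from medical records. What can be said is that no described form or schedule names the item.

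The analysis section also points to a Table 3-3 that is not in the available text. Nothing is assumed here about its content.

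**Conclusion.** The point holds as a matter of specification. The plan commits to an open covariate list that is long for 31 to 42 evaluable patients, includes an item with no described source, omits the T0 outcome, and is not carried into the Inferential Statistics text. The statistical harm is conditional on the model: substantial for an adjusted group effect tested with an uncorrected sandwich variance, absent from the error rate under a model-based t test (though the precision loss remains), and close to nil for group-by-time. The sizes rest on the assumed correlation, category counts, non-prognostic covariates and random dropout. The change is worth making on any of these readings, because the short T0-adjusted model is also more precise than the pre/post contrast (SE about 0.31 against 0.34 at N = 34).

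**What to change.** In III: Sample Size Calculation and in Inferential Statistics:

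1. Replace the list with a closed set, the T0 value of the outcome being analysed and age, and delete metastasis.
2. State that the test is the group effect on the post-baseline value or values, adjusted for T0.
3. State the variance method: a small-sample correction to the sandwich estimator, or a model-based t test.
4. Report the other demographic items descriptively in the baseline table.
5. Say whether baseline G-8 is used. Leaving it out costs little.

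No new data are needed. Two costs should be acknowledged. Chance imbalances in demographics would be described rather than adjusted for. T0 also becomes a covariate rather than a response, which changes the model and not only its wording, and a participant with T0 alone then contributes nothing to the Day 21 comparison. Under random 30% loss from 44, the T0-adjusted SE before adding age (0.316) is still below that of the pre/post contrast (0.349).

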Moreno-Morales et al., 2020), psychiatric patients (Carr et al., 2013; Gassner et al., 2022; Gold et al., 2009; Köhler et al., 2020; Marquez-Garcia et al., 2021), and children with autism (Mayer-Benarous et al., 2021). Research by Sezgin et al. (2022) indicates that interventions—including the use of instruments, classical, modern, or personalized music therapy—typically last between 20–45 minutes, are conducted 1–2 times per week, and continue for 1–2 months (Burns et al., 2008; Sezgin & Bektas, 2022).

Although many studies have found that music therapy can reduce depression, anxiety, and pain in cancer patients, its application for managing fatigue is less common. This review identified six clinical trials that utilized music therapy as an intervention for fatigue in leukemia patients. The frequency, duration, intervention methods, and outcomes of these studies are summarized below (see Table 2-4).

All six studies involved leukemia patients aged 18 or older undergoing chemotherapy. Four of these clinical trials reported significant differences (Burns et al., 2008; Cassileth et al., 2003; Reimnitz et al., 2020; Miladinia et al., 2021), finding small to large effect sizes (ES, $d = 0.12$ – 1.95).

- **Burns et al. (2008)** randomized 49 patients into a music therapy (MT) group (N=25) and a standard care group (N=24). The MT group received 20-minute sessions twice weekly for one month (eight sessions total). Using The Functional Assessment of Chronic Illness Therapy - Fatigue (FACIT-F) scale, they found a significant difference in fatigue between the groups, showing a small effect (Cohen's $d = 0.12$, $p < 0.001$).
- **Cassileth et al. (2003)** randomized 62 patients undergoing autologous stem cell transplantation (ASCT) into an MT group (N=34) and a standard care group (N=28). The MT group received 20-minute sessions of individualized live music (vocal and instrumental, based on patient preference) for 3–7 weeks. Fatigue, measured by the POMS-Fatigue subscale, decreased significantly in the MT group (Cohen's $d = 0.21$, $p = 0.03$).
- **Reimnitz et al. (2020)** randomized 35 leukemia patients to an MT group (N=18) or a standard care group (N=17). The MT group received two 30-minute individual sessions of live music. The Visual Analogue Scale - Fatigue (VAS-F) showed a significant difference between groups, demonstrating a moderate effect (Cohen's $d = 0.78$, $p = 0.004$).

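### The 34 patients follow from 0.21 entered as Cohen's f, while the protocol's review uses only Cohen's d; for an arm difference of 0.21 SD the power is about 9%, not 80%

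*Combined protocol and SAP*

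**What the plan says.** Section III, Sample Size Calculation, is the only place where the size is justified. It says: "The sample size was estimated based on the Generalized Estimating Equations (GEE) approach for repeated measures". The tool is named ("The calculation was performed using G*Power software (version 3.1.9.7"), with "a significance level (α) of 0.05", "statistical power ($1-\beta$) of 0.80" and an "anticipated effect size of 0.21. This calculation yielded a required sample size of 34 participants". The 34 patients are the number before attrition. The text does not say whether 0.21 is d, f or f², where it comes from, which G*Power test was run, how many measurements were entered, or what correlation was assumed. It points to Figure 3-2, which is not reproduced in the text available.

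The review of music-therapy trials (Section II of the music-therapy overview) uses one metric. It summarises the positive trials as "finding small to large effect sizes (ES, $d = 0.12$ – 1.95". Its only 0.21 belongs to the autologous stem-cell-transplantation trial, where fatigue "decreased significantly in the MT group (Cohen's $d = 0.21$, $p = 0.03". Cohen's f and a conversion from d to f appear nowhere.

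Table 1 schedules the fatigue NRS four times and the TFRS twice. The instruments section names the TFRS as the primary outcome measure. The inferential-statistics paragraph plans a GEE comparison of pre- and post-test values between the arms.

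**The concern.** A reader coming from the review will take 0.21 as a small standardized difference between arms, and will conclude that 34 patients give an 80% chance of detecting it. No two-arm comparison of this size does that. If 0.21 is on the f scale of a repeated-measures interaction test, the design is aimed at a much larger difference than the number suggests.

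This bears on how a null result is read. The analysis section relies on p < 0.05 and has no rule for a non-significant result. Readers who believe the trial had 80% power for a small effect could take such a result as evidence that music does not reduce fatigue, when the design could reliably see only a large effect.

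**Working it through.** **Inputs from the protocol.** Alpha 0.05, power 0.80, effect size 0.21, N = 34 (sample-size section); two equal arms; four NRS and two TFRS measurements (Table 1).

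**Assumed.** Two-sided testing, sphericity, and within-person correlation r = 0.5, with 0.3 to 0.7 as the range. The text gives none of these.

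**1. Reproducing 34.** For the repeated-measures group-by-time F test with m measurements and two groups:

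λ = f² · N · m / (1 − r), with df = (m − 1) and (N − 2)(m − 1).

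- f = 0.21, m = 4, r = 0.5, N = 34: λ = 0.0441 × 34 × 4 / 0.5 = 12.0, df = 3 and 96, power 82.3%.
- The same at N = 32: power 79.6%.

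So 34 is the smallest even total that reaches 80%. Other pairs come close to 34: three measurements with r between 0.5 and 0.6, or two with r between 0.6 and 0.7. In each of these 0.21 is still f.

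**2. Trying 0.21 as d.** A two-sample t test, or a change-score test at r = 0.5 (variance 2(1 − r) = 1), needs 357 per arm, or 714 in total. Adjusting for T0 (variance 1 − r² = 0.75) still needs about 268 per arm. Neither is near 34. Reading 0.21 as f² in a regression gives 40 (two-sided) or 31 (one-sided), so that does not match either.

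**3. What f = 0.21 means as an arm difference.** Let δⱼ be the arm difference in SD units at measurement j, with mean δ̄. The interaction f is the square root of the mean of ((δⱼ − δ̄)/2)².

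| Pattern of arm differences | f | d when f = 0.21 | Ratio to 0.21 |
|---|---|---|---|
| Two visits (0, d) | 0.25 d | 0.21/0.25 = 0.84 | 4.0 |
| Four visits, constant (0, d, d, d) | 0.2165 d | 0.21/0.2165 = 0.97 | 4.6 |
| Four visits, linear (0, d/3, 2d/3, d) | 0.1863 d | 0.21/0.1863 = 1.13 | 5.4 |

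**4. Power for d = 0.21 with 34 evaluable (17 per arm).** For the pre/post comparison, the noncentrality is 0.21 × √(17/2) / √(2(1 − r)). At r = 0.5 this is 0.61, against a critical t of 2.04 on 32 df, so power is 9%. It is 8% at r = 0.3 and 12% at r = 0.7. With a T0-adjusted comparison at r = 0.5 it is 11%. If all 44 or all 60 patients (the two recruitment totals in the protocol) were evaluable, the pre/post figure at r = 0.5 would be 10% or 13%.

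**5. The TFRS.** With two measurements, f = 0.21 and r = 0.5, λ = 0.0441 × 34 × 2 / 0.5 = 6.0 on 1 and 32 df. Power is 66%, and 80% would need N = 48. The difference detectable with 80% power at 34 is 0.99 SD for change and 0.86 SD if T0-adjusted.

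**6. Precision at 34 evaluable, r = 0.5.** The 95% CI half-width is 2.04 × √(2/17) = 0.70 SD for change, and 2.04 × √(0.75 × 2/17) = 0.61 SD if T0-adjusted.

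**The case against.** The strongest objection is that the mix-up is inferred. The sample-size section cites no trial and does not call 0.21 a d, and Figure 3-2 may show the test and its settings. If the sponsor chose f = 0.21 directly, 34 is correct G*Power output for four measurements at r = 0.5, and the gap is an undeclared metric and an unjustified assumption. This stands. A reader might infer that the transplantation trial's d was demonstrably typed into the f field; the documents make that likely but do not show it.

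The test is not uniquely identified either. A two-group within-factors test has the same formula, and there f is not an arm difference, so the conversions in step 3 hold only for the interaction test. The power for d = 0.21 in step 4 does not depend on this.

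The shortcut f = d/2 would make the assumed effect d = 0.42. It belongs to a between-group main effect, and that test needs 114 to 136 patients at r = 0.5 with two to four measurements, so it does not give 34.

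Three further readings go beyond the documents:

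- That the transplantation trial's d and p-value contradict each other. This would need p = 0.03 to come from an unadjusted comparison between arms, and the review does not say so.
- That the trial has only about one chance in ten of success. This applies only if the true difference is 0.21 SD. The review's range runs to 1.95, so a detectable 0.86 to 0.99 SD lies inside it.
- That 80% power is claimed for each laboratory value. The section lists them as dependent variables and makes no separate power claim.

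**Conclusion.** The concern holds. The stated 80% power does not apply to a standardized arm difference of 0.21, the reading that the protocol's own review invites. For that difference, power with 34 evaluable patients is about 9% (8 to 12% for r from 0.3 to 0.7). The figure of 34 arises with 0.21 as Cohen's f, which in the group-by-time test means an arm difference roughly four to five times as large. For the TFRS, measured twice, even f = 0.21 gives only 66% at r = 0.5.

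That 0.21 as d cannot give 34 is firm. The origin of 0.21 in the transplantation trial is a strong inference. The choice of four measurements and r = 0.5 is the simplest match to 34 but is not confirmed by the text.

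**What to change.** In the sample-size section, state that 0.21 is Cohen's f (the sponsor can confirm this from its G*Power output). Give its source, the G*Power test, the number of measurements and the assumed correlation. Restate the power as the arm difference that the design can detect, for example:

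> *With 34 evaluable patients the trial has 80% power for a Day 21 TFRS difference of about 0.99 SD (group-by-time, two visits, r = 0.5). Power for d = 0.21 is about 9%.*

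If the sponsor adopts a T0-adjusted comparison as the analysis, the two figures become about 0.86 SD and 11%. Say that the power statement applies to fatigue.

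In the inferential-statistics paragraph, add that a non-significant result will be reported with its 95% CI and will not be read as absence of effect. At 34 evaluable the expected half-width is about 0.7 SD for change, or 0.6 SD if T0-adjusted.

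The cost is a few sentences and a less favourable stated power or target effect. No extra patients are proposed.

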This study employs an **experimental research design** utilizing **randomized assignment** and **repeated measures**. Participants who consent to the study will be allocated to either the experimental group (Group A) or the control group (Group B). Group A participants will listen to self-selected music in addition to receiving standard care. Group B participants will receive standard care only. The objective is to evaluate the effectiveness of music therapy in alleviating fatigue. A total of 44 patients with leukemia undergoing their initial chemotherapy will be recruited, with 22 participants allocated to each group.

The measurement process will be conducted in two parts:

1. **Primary Data Collection:** Data will be collected at two main time points: upon admission for initial chemotherapy (Baseline, T0) and on Day 21 of the

chemotherapy cycle (T1). On Day 21, the researcher will visit the ward to collect the required data, including the Tang's Fatigue Scale, the Fatigue Numerical Rating Scale (NRS), and clinical laboratory data. If a participant has been discharged, data will be collected via telephone interview or an online questionnaire.

2. **Symptom Diary:** Participants will record their fatigue levels using the Fatigue NRS immediately following each music therapy session.

Baseline demographic data will be collected only at T0. The measurement time points and the application of corresponding instruments are detailed in Table 3-2.

Table 1: Schedule of Research Measurements

Time	Before Chemo (T0)	Chemo Day 7	Chemo Day 14	Chemo Day 21 (T1)
Tang's Fatigue Scale	○			○
Numerical Rating Scale (NRS)	○	○	○	○
WBC	○			○
Hemoglobin	○			○
Albumin	○			○
Demographic Data	○			

Note: ○ = Data to be collected

Research Setting and Participants

This study will be conducted in the hematology-oncology ward of a medical center located in Northern Taiwan. Participants must meet the following inclusion criteria:

1. Clinically diagnosed with Acute Myeloid Leukemia (AML) by a specialist physician.
2. Scheduled to receive initial (first-time) chemotherapy.
3. Aged 20 years or older.
4. Able to communicate in Mandarin or Taiwanese.
5. Possess normal hearing ability.
6. No history of psychiatric illness and clear consciousness.
7. No prior participation in any fatigue management intervention study.
8. Understands the research purpose, voluntarily agrees to participate, and has signed the informed consent form.

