will be categorized into four measurement scales: nominal, ordinal, interval, and ratio (Kaur et al., 2018). Nominal and ordinal scale data are considered **categorical variables** (e.g., sex, education level, occupation, perceived economic status, marital status, religious beliefs, and chemotherapy drug names) and will be presented as frequencies (n) and percentages (%). Interval and ratio scale data are considered **continuous variables** (e.g., age, fatigue severity, Absolute Neutrophil Count [ANC], hemoglobin, and albumin) and will be presented using means, standard deviations (SD), and ranges (minimum and maximum) (Kaur et al., 2018).

- **b. Inferential Statistics:** This study utilizes an experimental design with longitudinal follow-up and repeated measures, analyzed on an **intention-to-treat (ITT)** basis. It will compare the differences in fatigue severity and clinical laboratory values between the music therapy and control groups. During the study, data attrition may occur due to factors such as disease progression or a participant's personal decision to withdraw, leading to unequal sample sizes at different measurement points. Therefore, this study will employ **Generalized Estimating Equations (GEE)** to analyze the relationship between the independent and dependent variables. GEE will be used to compare pre- and post-test values (fatigue severity, Absolute Neutrophil Count [ANC], hemoglobin, and albumin) between the experimental and control groups. A *p*-value of < 0.05 will be considered the standard for statistical significance (Ziegler & Vens, 2010).

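### Recruitment is stated as both 44 and 60, and 44 less the plan's own 30% attrition leaves about 30 evaluable patients, not the 34 its 80% power claim requires

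*Combined protocol and SAP*

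**What the plan says.** The only power statement is in III: Sample Size Calculation. It gives G*Power, α = 0.05, power 0.80 and an effect size of 0.21, and concludes: "This calculation yielded a required sample size of 34 participants (as shown in Figure 3-2". It then says "To account for a potential attrition rate of 30%, the study aims to recruit a total of" 44, in two groups of 22. Research Design agrees: "A total of 44 patients with leukemia undergoing their initial chemotherapy will be recruited, with 22 participants allocated to each group". Research Procedures expects a total of 60 patients with AML "undergoing chemotherapy are expected to be recruited (n=30 per group").

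On outcomes, the sample size section says "The dependent variables are fatigue, White Blood Cell (WBC) count, hemoglobin, and albumin", and Research Instruments says "the TFRS was selected as the primary outcome measure for this study". Research Design states "Data will be collected at two main time points: upon admission for initial chemotherapy (Baseline, T0) and on Day 21". Table 1 places the TFRS and the laboratory values at those two points only. The fatigue NRS is the only outcome that Table 1 schedules at four (T0 and Days 7, 14 and 21). The analysis section says "GEE will be used to compare pre- and post-test values" between the groups.

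The readable text does not state the effect-size metric, the G*Power test, the number of measurements or the correlation between them. The text refers to Figure 3-2, which is not reproduced in the copy reviewed.

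**The concern.** Two things look wrong on the page. The plan gives two recruitment totals in current text. And the step from 34 to 44 inflates by 30% of the evaluable number, when the loss applies to the recruited number.

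A third may be wrong. The number 34 fits a four-visit calculation at a round correlation of 0.5, but the measure the plan calls primary has two visits.

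At stake is how the result will be read. A null TFRS result would be set against a claim of 80% power, so the claim should hold for that measure at the number of patients expected to remain. With both 44 and 60 stated, a reader cannot tell whether about 30 or 42 evaluable patients were planned.

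**Working it through.** **Inputs from the plan.** α = 0.05, power 0.80, effect size 0.21, required N = 34, attrition 30% and recruits 44 (sample size section); recruits 60 (Research Procedures); two visits for the TFRS and four for the NRS (Table 1).

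**Assumptions.** 0.21 is Cohen's f; the test is the within-between interaction of a repeated-measures ANOVA with two equal groups and sphericity; r is the correlation between visits; N rises in steps of 2; lost patients give no Day-21 data.

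**1. The plan's 34.** Noncentral F with λ = f²·N·m/(1 − r), df₁ = m − 1, df₂ = (N − 2)(m − 1), where m is the number of visits. With f² = 0.0441, m = 4, r = 0.5 and N = 34, λ = 0.0441 × 34 × 4/0.5 = 12.0 and power is 82.3%. N = 32 gives 79.6%, so 34 is reproduced. It is not a unique solution. N = 34 also results from three visits with r of about 0.56–0.58, or two visits with r of about 0.64–0.66. For four visits the band is about 0.47–0.50.

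**2. Attrition.**
- 34 × 1.3 = 44.2, which matches the stated 44.
- 44 × 0.70 = 30.8, or 30 in equal arms.
- 34/0.70 = 48.6, so 50 in equal arms.
- Loss that 44 can absorb: (44 − 34)/44 = 22.7%.
- 60 × 0.70 = 42.

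**3. Power at 30 on the plan's own calculation.** Putting N = 30 into the formula in step 1, over every band of r that returns 34, gives about 74–77% for two, three or four visits (76.6% for four visits at r = 0.5). This does not depend on which number of visits was used. At 42 the corresponding power is above 80%, because 42 exceeds 34 (90.4% for four visits at r = 0.5).

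**4. The two-visit TFRS (conditional).** With equal T0 means and a difference D (in SDs) only at Day 21, f = D/4, so f = 0.21 means D = 0.84 SD. The pre/post interaction uses step 1 with m = 2; at N = 34 and r = 0.5, λ = 0.0441 × 34 × 2/0.5 = 6.0. The T0-adjusted comparison is a noncentral t with n = N/2 per arm, ncp = D/[√(1 − r²)·√(2/n)] and df = N − 3; at N = 34 and r = 0.5, ncp = 0.84/(0.866 × 0.343) = 2.83.

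| Evaluable N | Pre/post, r = 0.3 / 0.5 / 0.7 | T0-adjusted, r = 0.3 / 0.5 / 0.7 |
|---|---|---|
| 30 | 47% / 60% / 82% | 64% / 73% / 87% |
| 34 | 52% / 66% / 87% | 70% / 78% / 91% |
| 42 | 61% / 76% / 93% | 80% / 87% / 96% |

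At r = 0.5, 80% power needs 48 patients (pre/post) or 36 (T0-adjusted). At N = 34, 80% is reached from r of about 0.64 (pre/post) or 0.53 (T0-adjusted).

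**5. Detectable difference at 80% power, T0-adjusted,** for r = 0.3, 0.5 and 0.7: 1.01, 0.92 and 0.76 SD at 30; 0.85, 0.77 and 0.63 SD at 42.

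**The case against.** The strongest objection concerns the visits. The G*Power settings may be in Figure 3-2, which cannot be seen, so they cannot be called missing or mismatched. Two visits at r of about 0.65 give the same 34. A four-visit calculation would not be foreign to the plan either: the sample size section says only fatigue, and the NRS has four scheduled visits. All of this stands, and the visit point is therefore only conditional.

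The shortfall also depends on r and on the analysis. With T0 adjustment and r = 0.5, 34 patients have 78%, close to 80%. With T0 adjustment and r = 0.65, even 30 patients have 83%. That stands too. However, the readable text states no r, and the covariates it names as examples are demographic and disease characteristics, not the T0 score.

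On attrition, it can be said that 44 still absorbs a 22.7% loss, and that discharged patients can be reached by telephone or online. But the 30% is the plan's own allowance, and 44 does not meet it. GEE does not repair this, because with two visits a patient without Day-21 data has no post-test TFRS value. No objection removes the conflict between 44 and 60.

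A reader might also notice that the literature review reports a Cohen's d of 0.21 for one earlier trial, and infer that this was entered as Cohen's f. The sample size section cites no source for its 0.21, so the documents do not support that inference and nothing here rests on it.

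**Conclusion.** Two errors hold without any assumption about visits or correlation. The recruitment total is stated as 44 and as 60. And 44 less 30% leaves 30.8 patients (30 in equal arms) against a requirement of 34. If lost patients give no Day-21 data, the plan's own type of calculation (interaction test, f = 0.21) then has about 74–77% power, not 80%. This shortfall belongs to the total of 44. If 60 is the intended total, 42 remain and the requirement of 34 is met.

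The visit mismatch is conditional. If 34 came from four visits at r = 0.5, the two-visit TFRS comparison at 0.84 SD has 66% power at 34 patients (78% T0-adjusted) and 60% at 30 (73%). A reader might infer that 34 was demonstrably computed for the wrong outcome, or that the TFRS simply has 66% power. The documents support neither: the settings are inferred, r = 0.5 is an assumption, and a two-visit calculation with r of about 0.64–0.66 explains 34 equally well.

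**What to change.** Agree one recruitment total and use it in Research Design, III: Sample Size Calculation and Research Procedures. In the sample size section, state the evaluable number after 30% loss (about 30 from 44, or 42 from 60). Keeping 34 evaluable would need 50 recruits in equal arms.

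For that evaluable number, give the power or detectable difference for the two-visit TFRS, naming the effect-size metric, the test, the visits and the assumed r. For example, with T0 adjustment at r = 0.5, 80% power is for 0.92 SD at 30 patients or 0.77 SD at 42, with the range for r = 0.3 to 0.7 shown beside it. If the T0-adjusted figure is used, add that adjustment to the inferential statistics section; the T0 TFRS is already collected. If the four-visit NRS was the measure powered, say so and give the TFRS figure separately. If Figure 3-2 already uses two visits and r of about 0.64–0.66, the text need only say so, and the attrition and total corrections still apply.

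The cost is one rewritten paragraph, one agreed total and possibly one sentence on T0 adjustment. The downside is a less favourable stated power or detectable effect. The restatement needs no extra patients; choosing a total above 44 would.
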